7.5.3.5 Sample Size Calculation

[figure not shown]
A sample size of at least 35 subjects with normal sinus node function and persistent 3rd degree AV block and at least 500 evaluable cardiac cycles during the auto setup and 20-minute resting period will provide greater than 90% power to reject the null hypothesis based on the following assumptions:

1. Two-sided type I error rate = 0.05
2. Single analysis after all enrolled subjects have had an opportunity to complete the MARVEL 2 study procedures and have had their Holter data evaluated
3. Each subject will have at least 500 evaluable beats during the auto-setup phase (VVI pacing) period and during VDD pacing during the 20-minute resting period
4. The proportion of subjects meeting the primary efficacy endpoint in one pacing mode, but not the other (i.e. proportion of discordant pairs) will exceed 50%
5. At least 90% of discordant subjects will favor the MARVEL 2 features

Justification of Sample Size Assumptions

Figure 9 displays the AV synchronous pacing percentage observed in the MARVEL study by predominant rhythm. The average AV synchronous pacing percentage among the 33 subjects with a predominant rhythm of high-grade AV block was 80.0% during MARVEL adaptive mode (VDD pacing) compared to 37.5% during VVI pacing ($P < 0.001$). Among the 33 subjects with a predominant rhythm of high-grade AV block, 72.7% of subjects (24 of 33) had an AV synchronous pacing rate exceeding 70% while in MARVEL adaptive mode compared to 6.1% (2 of 33) during MARVEL monitor mode (VVI pacing).

Figure 9: AV Synchronous Pacing Percentage Observed in the MARVEL Study by Predominant Rhythm

7.5.3.6 Determination of Subjects/Data for Analysis

All subjects with normal sinus node function and persistent 3rd degree AV block during Holter monitoring with at least 500 evaluable beats during VVI pacing and at least 500 evaluable beats during MARVEL 2 adaptive pacing in which the device is providing VDD pacing will be included in the primary analysis for this objective. For *de novo* subjects, only data collected during the 20-minute resting period at the pre-hospital discharge procedure will contribute to the analysis of the primary objective.

However, if a *de novo* subject does not have usable Holter data from the pre-hospital discharge procedure, their Holter data at the 1-month post-implant procedure will be used in the analysis, if available.

As described in section 7.5.3.4 cardiac cycles with no ventricular sense or pace markers and indication of telemetry dropout in the first 300 ms following a P-wave as well as P-waves that occur during an AV conduction check will be excluded from the primary analysis (i.e. they are not evaluable beats).

7.5.3.7 Missing Data and Sensitivity Analyses

Missing Data

Given the relatively short duration of the study, missing data is not expected to be a serious issue. Since telemetry dropout may influence the number of evaluable beats for a subject during both VVI pacing

and MARVEL 2 adaptive pacing, the total number of heart beats and total number of evaluable beats will be summarized.

Missing Data Sensitivity Analyses

If any subjects with normal sinus node function and persistent 3rd degree AV block do not have usable Holter data during the study, the reason the Holter data was not usable will be discussed. Additionally, to address concerns with missing data that may arise, sensitivity analyses will be performed to assess the robustness of the observed statistical inference with respect to the missing data.

The first sensitivity analysis will be to include all subjects with normal sinus node function and persistent 3rd degree AV block that had some usable Holter data during both 20-minute resting period (MARVEL 2 adaptive pacing) and VVI pacing control period (i.e. auto-setup phase) regardless of the number of evaluable beats in each phase.

The second sensitivity analysis will include all subjects who had the MARVEL 2 software downloaded and had a Holter monitor placed on them that were classified as having a predominant rhythm of persistent 3rd degree AV block with normal sinus function or who did not have their rhythm classified. This sensitivity analysis will incorporate a tipping point methodology. Specifically, all subjects with missing data will be included as meeting the primary efficacy endpoint during MARVEL 2 adaptive pacing and not meeting it during VVI pacing (i.e. discordant in favor of MARVEL 2 adaptive pacing) and then iteratively changed to not meeting the endpoint during MARVEL 2 adaptive pacing and meeting it during VVI pacing (i.e. discordant in favor of VVI pacing). The tipping point will be defined as the number of subjects of the total with missing data that would have to shift from being discordant in favor of MARVEL 2 pacing to discordant in favor of VVI pacing to change the statistical inference. If the tipping point is less than the number of subjects with missing data stochastic methods may be used to aid in interpreting the likelihood of meeting or exceeding the tipping point as follows. Using the observed data, the beta distribution will be used to draw the probability a subject with missing data has normal sinus node function and persistent 3rd degree AV block. Next, the Dirichlet distribution with shape parameters corresponding to the observed 2×2 table will be used to draw the probability that the subject with missing data would be in the table cell that is discordant and in favor of VVI pacing. The product of these two probabilities will be used to determine the number of subjects with missing data that would end up in the discordant cell in favor of VVI pacing. Monte-Carlo sampling will be used to determine the probability that the tipping point is met or exceeded.

Other Sensitivity Analyses

Since *de novo* subjects may have more than one visit in which both the AV synchronous pacing percentage is evaluated in both VVI and MARVEL 2 adaptive mode, the primary efficacy endpoint will also be compared utilizing usable Holter data from all study visits for subjects with normal sinus node function and persistent 3rd degree AV block. Specifically, a logistic regression model utilizing GEE to account for correlation in outcomes within subject will be used to estimate the effect of MARVEL 2 adaptive pacing on the primary efficacy endpoint. Specifically, the response for this model will be the primary efficacy endpoint status (1=met primary efficacy endpoint, 0=did not meet primary efficacy endpoint) and the independent variable will be pacing mode (VVI or MARVEL 2 adaptive mode). An exchangeable working correlation matrix will be employed with subjects considered repeated across

pacing mode and study visit. The SAS code for implementing the model is similar to that shown above for the subgroup analyses with the exception that the indicator for adaptive mode pacing would be the only covariate.

[Redacted]

[Redacted]

[Redacted]

[Redacted]

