2. P-waves that occur during an AV conduction mode switch as these P-waves occur when the pacing mode is set temporarily to VDI40 while the device checks for intrinsic AV conduction. These are identified from the accuracy spreadsheet where a supplemental marker in the preceding P-P interval (column 15 (O) < P-P interval), and the pacing mode in the supplemental marker is VDI40, indicating a mode switch (column 17 (Q) = 7). Note that for the pacing mode, the supplemental marker indicates the pacing mode on the next ventricular event, which is why a look-back to the preceding supplemental marker is necessary to determine if the current ventricular event is in a mode-switched state.

All other P-waves in the accuracy spreadsheet will be considered evaluable. Evaluable P-waves will be considered synchronous if they occur within 300 ms of the following ventricular event. Thus, evaluable P-waves will be considered synchronous if column 2 (B) < 0.3 and asynchronous if column 2 (B) \geq 0.3.

For the analysis of the primary efficacy objective, P-waves with records in the accuracy spreadsheet corresponding to the auto setup phase (i.e. columns 11 (K) and 12 (L) indicate auto setup phase) or

resting phase (i.e. columns 11 (K) and 12 (L) indicate auto setup phase) will be selected. The auto setup phase will occur during MARVEL 2 monitor mode pacing (i.e. VVI pacing) and the resting phase will occur during MARVEL 2 adaptive mode pacing (i.e. VDD pacing). If at least 70% of evaluable beats are considered synchronous during the VVI or MARVEL 2 adaptive pacing mode during resting, then the subject will be considered to have met the primary efficacy endpoint during the VVI or MARVEL 2 adaptive pacing mode during rest respectively. McNemar's test for paired proportions will be used to test the primary efficacy objective hypothesis. Note that subjects with fewer than 500 evaluable beats during each period will be excluded from the primary efficacy analysis.

[REDACTED]

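### The efficacy tipping-point analysis imputes both pacing modes together, so it can contradict a mode result that was observed and misstate the tipping count

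*SAP*

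**What the plan says.** SAP 7.5.3.6 admits a subject to the primary efficacy analysis only "with at least 500 evaluable beats during VVI pacing and at least 500 evaluable beats during MARVEL 2 adaptive pacing". Failing either count is enough for exclusion.

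SAP 7.5.3.7 then gives two missing-data analyses. The first adds subjects with some usable data in both periods, whatever the beat count. The second takes everyone who had the download and a Holter and was either classified as 3rd degree block with normal sinus function or not classified. In it, "all subjects with missing data will be included as meeting the primary efficacy endpoint during MARVEL 2 adaptive pacing" and as not meeting it in VVI. Subjects are then switched one at a time to the reverse pattern. The tipping point is the number of switches that changes the inference. If that number is below the number missing, a beta and a Dirichlet draw may be used to judge how likely it is to be reached. Protocol 17.5.6 has the same rule without the simulation detail.

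No visible text defines missing data by mode, or says what happens to a subject with one mode observed. Parts of SAP 7.5.2 and 7.5.3 are redacted and cannot be checked.

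**The concern.** Each subject contributes two results, and either can be lost alone. VVI is recorded during auto-setup and the adaptive rest period follows, so telemetry can fail in one and not the other. Read literally, the rule ignores whichever result was obtained.

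There are two kinds of conflict:

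- **Adaptive observed as not met, VVI missing.** The start state scores the subject as an adaptive success. The data allow only a concordant pair or a VVI-favouring pair.
- **VVI observed as not met, adaptive missing.** The end state scores the subject as a VVI success. The data allow only a MARVEL-favouring pair or a concordant pair.

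The mirror cases behave alike: VVI observed as met acts like the first, adaptive observed as met like the second. The second analysis is the only one that covers subjects with no usable data in one mode, in a study meant as pivotal evidence. At stake is how robust the efficacy result is reported to be.

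**Working it through.** **Inputs.** SAP 7.5.3.5: "Two-sided type I error rate = 0.05"; 35 subjects; half of pairs discordant; "At least 90% of discordant subjects will favor the MARVEL 2 features". SAP 7.5.3.4: McNemar's "test for paired proportions will be used to test the primary efficacy objective hypothesis"; the visible text does not say which version, so asymptotic (no continuity correction) and exact are both shown. The numbers missing, and of each type, are not in the documents and are assumptions here.

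**The plan's own figure.** The SAP says 35 subjects "provide greater than 90% power to reject the null hypothesis". With the discordant count d ~ Binomial(35, 0.5) and the favourable count ~ Binomial(d, 0.9), power is 96.9% asymptotic and 94.8% exact. The claim reproduces.

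**Planning table.** 35 × 0.5 = 17.5, about 18 discordant; 18 × 0.9 = 16.2, so about 16 vs 2.

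**Formulas.** Let b and c be the observed discordant counts (MARVEL-favouring, VVI-favouring), m the number missing and k the number flipped. The tipping count is the smallest k with p ≥ 0.05. The asymptotic statistic is (b − c)²/(b + c), and the table after k flips is:

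- as written: (b + m − k, c + k)
- all missing have adaptive observed as not met: (b, c + k)
- all missing have VVI observed as not met: (b + m − k, c)

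In the last case the worst table is (b, c) itself. A significant result therefore never tips.

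**Overstatement at 16 vs 2, all missing with adaptive observed as not met** (as written / observed mode held):

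| m | asymptotic | exact |
|---|---|---|
| 4 | never / never | 4 / 4 |
| 5 | 5 / 5 | 5 / 4 |
| 6 | 6 / 5 | 5 / 4 |
| 7 | 6 / 5 | 6 / 4 |
| 8 | 7 / 5 | 6 / 4 |

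- m = 8, asymptotic, as written: 18 vs 8 gives 100/26 = 3.85, p = 0.0499 (only just significant); 17 vs 9 gives 64/26 = 2.46, p = 0.117. Tips at 7.
- m = 8, asymptotic, held: 16 vs 6 gives 100/22 = 4.55, p = 0.033; 16 vs 7 gives 81/23 = 3.52, p = 0.061. Tips at 5.
- m = 7, exact, as written: 18 vs 7 has p = 0.043 and 17 vs 8 has p = 0.108. Tips at 6.
- m = 7, exact, held: 16 vs 5 has p = 0.027 and 16 vs 6 has p = 0.052. Tips at 4.

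The same gaps (7 against 5; 6 against 4) arise if only 3 of the missing are of this type and the rest lack both modes.

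**Understatement at 16 vs 2.** Some missing subjects have VVI observed as not met; the rest lack both modes.

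- Asymptotic, 9 missing, 4 of this type: 7 as written, 9 held.
- Exact, 8 missing, 4 of this type: 6 as written, 8 held.
- Asymptotic, 5 missing, 1 of this type: the written rule tips at 5 of 5 (16 vs 7, p = 0.061). The worst table the data allow is 16 vs 6, p = 0.033, so it cannot tip. With the exact test both rules tip at 5.

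**Weaker results than planned** (as written / all adaptive observed as not met / all VVI observed as not met; both tests agree):

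- 10 vs 2, 5 missing: 3 / 1 / never. Here 12/35 = 34% are discordant.
- 13 vs 4, 8 missing: 4 / 1 / never. Here 13/17 = 76% favour MARVEL 2.

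**Strong result.** MARVEL's margins (24 of 33 above 70% in adaptive, 2 of 33 in VVI) fix b − c at 22. For a nearby table of 22 vs 1 with 8 missing, the fully flipped table is 22 vs 9: 169/31 = 5.45, p = 0.020 (exact 0.029). Nothing tips.

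**Simulation step.** The Dirichlet draw uses the whole 2×2 table. For a subject with VVI observed as not met, the VVI-favouring cell has probability zero. For a subject with adaptive observed as not met, that cell's probability must be divided by the adaptive failure rate. At MARVEL's 9 of 33 this multiplies it by 33/9, about 3.7.

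**The case against.** Several counter-arguments have force.

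- **The first sensitivity analysis already uses some of these subjects.** Someone with ample adaptive beats and, say, 450 VVI beats enters it with the observed adaptive result. This stands. The gap is left for subjects with no usable data in one mode, and for the conflict between the two analyses over low-beat subjects.
- **Missing may have been meant as no usable Holter at all.** The beta draw for rhythm suits unclassified subjects, who would usually lack VVI data too, and for subjects missing both modes the full swing is right. A classified subject may also lack a VVI result, since SAP 7.5.5.6 says rhythm does not need the marker channel. This is a possible reading, but the rule says all subjects with missing data and the term is undefined.
- **One-mode loss may be rare.** A reader might infer that many missing subjects will have one complete mode. The documents do not support that. They give no count, they expect little missing data, and one Holter records both periods.
- **The rule is conservative at its limit.** A reader might infer that it could hide a reversible result. It cannot. The fully flipped table (b, c + m) is at least as adverse as any table the observed modes allow, and McNemar's p-value rises as b falls or c rises. Only the count, and the optional simulation built on it, can err favourably.

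**Conclusion.** The point holds as a statement of what can happen under the literal rule. Subjects with one observed mode can be put in cells their data exclude, and the tipping count can be wrong in either direction. Understatement is the likelier direction, because 31 of 33 MARVEL subjects did not exceed 70% in VVI.

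The size is modest. In the all-adaptive-failure extreme at about 16 vs 2, the count is off by at most one up to 6 missing, and by two from 7 (exact) or 8 (asymptotic) missing. Larger relative errors need a weaker result than planned. At 22 vs 1 with up to 8 missing there is no effect. It would be wrong to infer that the count is routinely two or more off. That depends on assumed numbers of missing and one-mode subjects.

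The primary test, its alpha and its power are untouched, and a conclusion that the result does not tip is safe. This is worth correcting because a plainly better rule is available at almost no cost.

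**What to change.** In SAP 7.5.3.7 and protocol 17.5.6:

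1. Define missing separately for each mode.
2. Hold fixed any mode result observed on at least 500 evaluable beats, and vary only the missing mode.
3. Use the full swing from MARVEL-favouring to VVI-favouring only for subjects missing both modes.
4. In the SAP simulation step, condition the Dirichlet draw on the observed mode.
5. Report how many subjects are missing VVI only, adaptive only, and both.

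The cost is a sentence or two of wording and a small programming change. No new data are needed.

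### The optional Monte Carlo step of the efficacy tipping-point analysis compares mismatched counts, so it can only understate the chance that missing data overturn a borderline result

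*SAP*

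**What the plan says.** SAP 7.5.3.7 describes a second sensitivity analysis for the primary efficacy objective. It covers subjects with software downloaded and a Holter placed who were classified as persistent 3rd degree AV block with normal sinus function, or whose rhythm was not classified. The starting position is that "all subjects with missing data will be included as meeting the primary efficacy endpoint during MARVEL 2 adaptive pacing and not meeting it" in VVI mode. Subjects are then moved one at a time to the opposite discordant cell. The tipping point is the number of moves that changes the inference.

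If the tipping point is smaller than the number missing, a simulation may be run as an aid to interpretation. It draws, from a beta distribution, the probability that a missing subject has the target rhythm. It then uses "the Dirichlet distribution with shape parameters corresponding to the observed" 2×2 table to draw the probability of the VVI-favouring discordant cell. The last steps are: "The product of these two probabilities will be used to determine the number of subjects with missing data that would end up in" that cell, and a Monte Carlo estimate of how often the tipping point is reached. No added constant or prior is stated, and McNemar's test is not recomputed on a completed table. Protocol 17.5.6 mentions stochastic methods without detail, so the SAP text is the only specification.

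**The concern.** Write b for subjects who meet the endpoint only in MARVEL 2 adaptive mode, c for those who meet it only in VVI, m for the number missing and k for the tipping point. The threshold k is calculated with the other m − k missing subjects sitting in the b cell. The simulation draws something different: many of those subjects are outside the target population or concordant, and neither kind enters McNemar's test. Comparing the simulated count with k still treats them as MARVEL 2 wins. The less likely a missing subject is to belong in the analysis, the safer the result appears.

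The step exists only to say how likely it is that missing data would overturn the efficacy result. A figure that is too low by construction could reassure a reader about a result that is in fact sensitive to the missing subjects.

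A second, separate point: if the Dirichlet shapes are the raw cell counts and c = 0, the VVI-favouring probability is undefined or fixed at zero.

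**Working it through.** **Inputs from SAP 7.5.3.5.** "Two-sided type I error rate = 0.05"; at least 35 subjects; half of the pairs discordant; "At least 90% of discordant subjects will favor the MARVEL 2 features". The planned table is therefore b = 35 × 0.5 × 0.9 = 15.75 (about 16) and c = 35 × 0.5 × 0.1 = 1.75 (about 2).

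**The plan's own figure.** The SAP says the sample "will provide greater than 90% power to reject the null hypothesis based on the following assumptions". With D ~ Bin(35, 0.5) discordant pairs and b ~ Bin(D, 0.9), power is 94.8% (exact McNemar), 96.9% (asymptotic) or 94.0% (continuity-corrected). The claim reproduces.

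**Assumptions, because the documents do not give them.** Observed tables; m (at most about 100 − 70 = 30 from the enrolment cap and the usable-dataset target); eligibility either Beta(35,35), from 35 of 70, or certain; exact McNemar, since the SAP does not name the version; and a binomial draw from the product of probabilities.

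**Direction of the error.** If x ≥ k missing subjects fall in the VVI-favouring cell, the completed table has c + x against at most b + m − x. That is no better for MARVEL 2 than c + k against b + m − k, which is already non-significant. So every draw the SAP counts as tipped is lost on the completed table too. The converse fails, so the SAP figure can only be too low.

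**Worked example: b = 10, c = 2 (p = 0.039), n = 35, m = 10.** Starting from 20 vs 2, three flips give 17 vs 5 (p = 0.017) and four give 16 vs 6 (p = 0.052), so k = 4. Yet one VVI-favouring subject, with the other nine ineligible or concordant, gives 10 vs 3 (p = 0.092): significance is lost, but the SAP step records no tipping.

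Hand check at the mean probabilities with half eligible. VVI-favouring: 0.5 × 2/35 = 0.0286. MARVEL-favouring: 0.5 × 10/35 = 0.143.

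- SAP rule: P(X ≥ 4) ≈ 210 × 0.0286⁴ × 0.971⁶ ≈ 0.0001. Letting the probabilities vary across draws raises this to about 0.06% to 0.1%.
- Completed table, X = 1: probability 10 × 0.0286 × 0.971⁹ ≈ 0.220. Significance is lost if at most one of the other nine favours MARVEL 2 (11 vs 3, p = 0.057; 12 vs 3, p = 0.035). Each does so with probability 0.143/0.971 = 0.147, giving 0.853⁹ + 9 × 0.147 × 0.853⁸ ≈ 0.61. Contribution 0.134.
- Completed table, X = 2: probability 45 × 0.0286² × 0.971⁸ ≈ 0.029. Significance is lost if at most two of the other eight favour MARVEL 2 (12 vs 4, p = 0.077; 13 vs 4, p = 0.049), probability about 0.90. Contribution 0.026.
- X ≥ 3 adds about 0.002. Total about 16%.

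**Simulated results** (40,000 to 60,000 draws, raw-count shapes). Each cell shows the SAP rule, then the completed table.

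| Observed b vs c | n | m | k | Beta(35,35) | All eligible |
|---|---|---|---|---|---|
| 10 vs 2 (p = 0.039) | 35 | 10 | 4 | 0.06%, 16% | 0.8%, 15% |
| 8 vs 1 (p = 0.039) | 25 | 10 | 4 | 0.03%, 11% | 0.4%, 10% |
| 13 vs 4 (p = 0.049) | 35 | 5 | 2 | 3.5%, 21% | 11%, 26% |
| 16 vs 2 (p = 0.001) | 35 | 10 | 7 | under 0.1% both | under 0.1% both |

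The asymptotic test shows the same pattern: 9 vs 2 (p = 0.035) with 10 missing gives 0.01% against 16.9%. For 16 vs 2 with up to 30 missing, the completed-table figure is at most 0.3%.

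**Empty cell.** For 6 vs 0 (p = 0.031), n = 35, m = 10, raw-count shapes give exactly 0 under both rules, so completing the table does not cure this defect. With 0.5 added per cell and the Beta draw, the SAP rule gives about 0.01% and the completed table 5.0%.

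**The case against.** The strongest reply is that little turns on this number. The step is optional and interpretive, and no success criterion uses it. McNemar's test, the sensitivity analysis that ignores the 500-beat minimum, and the deterministic tipping point all stand; in the worked example a reader would still see that 4 flips among 10 missing overturn the result. Missing data are not expected to be serious. Under the planning assumptions, a significant result with p between 0.02 and 0.05 has only about 7% probability, and the earlier MARVEL study (24 of 33 meeting the threshold in adaptive mode against 2 of 33 in VVI) points to a stronger result. All of this stands and limits the consequence. It does not make the stated rule correct.

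Three stronger readings are tempting and should be resisted.

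- A reader might infer that the step runs only when the result is fragile. It does not: 16 vs 2 with 10 missing has k = 7, below 10, so the condition is met where both methods give about 0.
- A reader might take the chance of an empty VVI-favouring cell under the planning assumptions, 0.95³⁵ = 16.6%, as the chance of a misleading zero. That figure covers every value of b. The chance that c = 0 and b is 6 or 7 is about 0.01%; when c = 0, b is usually near 16 and a reported zero is essentially right.
- A reader might take the zero as certain. The SAP says the shapes correspond to the observed table; it does not say that they are raw counts with nothing added. That is the literal reading, but not the only one.

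**Conclusion.** The mismatch follows from the SAP text as written. The threshold credits all unflipped missing subjects to MARVEL 2, while the draws make many of them ineligible or concordant. The error has one direction, towards reassurance. In the borderline tables examined, the step reports about 0.03% to 11% where its own model implies about 10% to 26%; at the planned effect the difference is negligible. These sizes rest on the assumed tables, numbers missing, eligibility distribution and exact test; the direction does not.

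The empty-cell problem is a separate, conditional defect that matters only when the MARVEL-favouring count is also small.

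The documents do not support a claim that the primary efficacy inference is wrong or at risk from this step. What is wrong is one supporting probability, in the situation where a reader would most want to rely on it. It should be corrected before the analysis.

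**What to change.** Replace the product-of-probabilities step in SAP 7.5.3.7. In each draw:

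1. Keep as eligible every missing subject already classified as persistent 3rd degree AV block with normal sinus function. Draw eligibility from the Beta only for subjects with unclassified rhythm, and drop those drawn ineligible. Drawing eligibility for everyone would randomly delete known members of the target population.
2. Allocate the eligible subjects across all four cells from a Dirichlet whose shapes are the observed counts plus a stated small constant, for example 0.5 per cell. The Beta parameters should be stated as well.
3. Recompute McNemar's test on the completed table, using the same version as the primary analysis.
4. Report the share of draws in which significance in favour of MARVEL 2 is lost.

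The deterministic tipping point can stay as it is. The cost is a few lines of SAP text and code, with no new data. The constant is a choice among several, so it should be fixed in advance. The reported probability of tipping will be less favourable than under the present rule.
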